2.6 Sample Size and Power

A total of 25 evaluable patients per arm will provide 71.8% power for each test comparing a dose with control via a Fisher's exact test at I-sided alpha = 0.15 to detect a difference between a control proportion 0.55 and an experimental dose proportion 0.80; these tests will be conducted in a fixed sequence: higher dose versus control first and lower dose versus control second, with the second test considered exploratory (failed) if the first test fails.

3 EFFICACY AND SAFETY VARIABLES

3.1 Primary Efficacy Endpoint(s)

The primary endpoint is the rate of patients in each treatment group achieving morphological CR based on IWG criteria during the induction and re-induction phases of the treatment. Morphologic CR is defined as ANC >1000/ μ L, platelet count >100,000/ μ L, <5% blasts in a bone marrow aspirate sample, no blasts with Auer rods, and no evidence of extramedullary disease (see Appendix A of protocol). Note that a patient is only considered to have achieved morphologic CR if this is documented on or after 21 days from date of randomization and not superseded by a subsequent data entry within 42 days of randomization that indicates treatment failure or progressive disease or persistent disease as indicated by >5% blasts in a bone marrow aspirate sample.

3.2 Secondary Efficacy Endpoints

- Event Free Survival (EFS)
 - Event-free survival (from date of randomization) is measured from the date of randomization until treatment failure (e.g., failure to achieve composite complete morphological remission during the induction or re-induction phase of the study lasting up to 60 days, relapse from CR, or death from any cause, whichever occurs first).

- Leukemia-Free State (LFS)
 - Leukemia-free survival is only assessed in patients who achieve composite CR and is measured from the date of leukemia-free state until disease relapse or patient death from any cause, whichever occurs first.

- Overall Survival (OS)
 - Overall survival is measured from the date of randomization until death from any cause.

- Composite Complete Remissions (CR) rate
 - Complete remission rate includes CR, (on or after 21 days from date of randomization) and CRi and CRp (either need to be on or after 21 days from date of randomization) as defined by IWG criteria (Appendix A in the protocol) during the induction and re-induction phases of treatment. If a patient achieves a composite CR, but followed by PD or treatment failure from day 21 to 42, then the patient did not achieve a composite CR and should be considered a treatment failure.

- Duration of morphologic CR
 - Duration of morphologic complete response is measured from the achievement of CR to detection of relapse. A relapse is defined as progressive disease or death from clinical disease progression

- Duration of composite CR (if available)
 - Duration of composite complete response is measured from the date of achievement of composite CR to detection of relapse. A relapse is defined as either progressive disease or death from clinical disease progression.

- 30-day, 60-day and 90-day mortality
 - Thirty-day, 60-day, and 90-day mortality are the rate of death during 30 days, 60 days, and 90 days, respectively, from the first day of induction treatment.

- Neutrophil and Platelet Recovery
 - Time to neutrophil recovery (from date of randomization) is measured from the date of randomization until ANC recovers to > 500 and >1000/ μ L respectively.

- o Time to transfusion-independent platelet recovery (from date of randomization) is measured from the date of randomization until the first day that the platelet count recovers to $> 20,000$ and $> 100,000/\mu\text{L}$ respectively (provided it is not as a consequence of platelet transfusion and provided platelets are then maintained at $> 20,000$ and $> 100,000/\mu\text{L}$ respectively for the five subsequent days without platelet transfusion).

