6.4 TREATMENT OF PATIENTS

6.4.1 Treatments Administered

For induction therapy, all patients will receive standard idarubicin + cytarabine chemotherapy. Patients randomized to Groups 2 and 3 will also receive CX-01. CX-01 will be continually infused while idarubicin will be administered per institutional standard.

Group 1: Idarubicin + Cytarabine

- Idarubicin 12 mg/m²/day by slow (10 to 30 minutes) IV injection/infusion daily on Days 1, 2, and 3
- Cytarabine 100 mg/m²/day by continuous 24-hour IV infusion on Days 1-7.

Group 2: Idarubicin + Cytarabine + plus lower dose CX-01

- CX-01 given as a 4 mg/kg initial bolus on Day 1 only, 30 minutes after completion of administration of the first dose of idarubicin, followed by CX-01 0.125 mg/kg/hour as a continuous 24-hour IV infusion on Days 1-7
- Idarubicin 12 mg/m²/day by slow (10 to 30 minutes) IV injection/infusion daily on Days 1, 2, and 3
- Cytarabine 100 mg/m²/day by continuous 24-hour IV infusion on Days 1-7.

Group 3: Idarubicin + Cytarabine + plus higher dose CX-01

- CX-01 given as a 4 mg/kg initial bolus on Day 1 only, 30 minutes after completion of administration of the first dose of idarubicin, followed by CX-01 0.25 mg/kg/hour as a continuous 24-hour IV infusion on Days 1-7
- Idarubicin 12 mg/m²/day by slow (10 to 30 minutes) IV injection/infusion daily on Days 1, 2, and 3
- Cytarabine 100 mg/m²/day by continuous 24-hour IV infusion on Days 1-7.

Re-induction Therapy

A bone marrow aspirate and biopsy will be performed between Days 14-21 of the induction cycle. If bone marrow shows leukemia-free state, i.e. less than 5% blasts in a aspirate sample, no further chemotherapy will be given until recovery of blood counts. If the bone marrow shows more than 5% blasts, a re-induction cycle may be given as outlined above. If the Days 14-21 marrow is indeterminate e.g., if there is a question of residual leukemia, a bone marrow aspirate may be repeated 7 days later for confirmation. Re-induction will be given with the same assigned regimen ("7 + 3" ± CX-01) as

administered during the first induction cycle as outlined above.

If in the Investigator's opinion, the patient is not fit to receive full re-induction cycle of "7 + 3" ± CX-01 at the Investigator's discretion the patient may receive "5 + 2" ± CX-01 which is 5 days of cytarabine and 2 days of idarubicin as outlined below:

Group 1: Idarubicin + Cytarabine

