10. APPENDICES

APPENDIX A – Acute Myeloid Leukemia Response Criteria

The IWG consensus criteria for treatment response in AML will be used to evaluate response to treatment.

Definitions of Remission

Morphologic complete remission (CR): ANC >1000/ μ L, platelet count >100,000/ μ L, <5% bone marrow blasts, no Auer rods, no evidence of extramedullary disease.

Morphologic CR with incomplete blood count recovery (CRi): CRi, which is CR without recovery of neutrophils and/or platelets (ANC may be <1000 μ L and/or platelet count <100,000/ μ L).

Partial remission (PR): ANC >1000/ μ L, platelet count >100,000/ μ L and at least a 50% decrease in the percentage of marrow aspirate blasts to 5 to 25%, or marrow blasts <5% with persistent Auer rods.

Progressive Disease

Progressive disease (PD) is defined as any one of the following:

- More than 50% increase in bone marrow blast % from best assessment (with a minimum threshold of 20% blasts in the marrow).
- >50% increase in circulating malignant blasts (with absolute blasts >1000/ μ L).
- Development of biopsy-proven extramedullary leukemia (if the patient has extramedullary disease at baseline then PD will be defined by blood and marrow criteria or if new sites of extramedullary disease appear).

In patients who present with initial marrow blast percentage sufficiently high to preclude the ability to base disease progression on a >50% increase in marrow blast percentage; disease progression should be based on peripheral blood criteria or development of extramedullary leukemia.

Stable Disease

Patients who fail to achieve CR, CRi or PR and who do not have criteria for PD will be defined as having stable disease. If the patient dies prior to response assessment at the end of Cycle 1, then they will be classified as “Indeterminate”.

Relapse from CR or CRi

Reappearance of leukemia blasts in the peripheral blood; or >5% blasts in the bone marrow not attributable to another cause (e.g., recovery of normal cells following chemotherapy-induced aphasia); or appearance or reappearance of extramedullary disease and the bone marrow blast percentage is >5% but < or equal to 20%, than a repeat bone marrow performed at least 7 days after the first marrow examination and documenting bone marrow blast percentage is >5% is necessary to establish relapse.

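### SAP 3.2 lets an interim leukemia-free marrow in aplasia be scored as composite CR, chiefly after a 7-day repeat marrow or in re-induction

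*SAP*

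**What the plan says.** - **Composite CR (SAP 3.2).** Besides CR it counts "CRi and CRp (either need to be on or after 21 days from date of randomization) as defined by IWG criteria (Appendix A". One reversal rule follows: a composite CR "followed by PD or treatment failure from day 21 to 42, then the patient did not achieve a composite CR".
- **Primary CR (SAP 3.1).** The reversal rule is wider. It also names "persistent disease as indicated by >5% blasts in a bone marrow aspirate sample".
- **CRi (Protocol Appendix A).** "CRi, which is CR without recovery of neutrophils and/or platelets". Neither count has a lower limit. There is no separate leukemia-free category and no definition of CRp. Progression in the marrow needs a rise of more than 50% from best and at least 20% blasts.
- **Early marrow (Protocol 6.4.1, Days 14-21).** "If bone marrow shows leukemia-free state, i.e. less than 5% blasts in a aspirate sample, no further chemotherapy will be given until recovery". If the result is indeterminate, "a bone marrow aspirate may be repeated 7 days later for confirmation". Table 6—1 applies the same schedule to re-induction.
- **Remission evaluation (Protocol 6.4.1).** This is a separate step: at count recovery or, without recovery, at about Day 35 after one course and about Day 49 after re-induction. Table 6—1, footnote 14, also has a Day 42 marrow if counts have not recovered.
- **Use of composite CR.** Failure to reach it is an EFS event, and reaching it defines the LFS set (SAP 3.2). CRi and composite CR are analysed in the same way as the primary endpoint (SAP 7.6.2 and 8).

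**The concern.** Remove the count requirement from CR, as Appendix A does for CRi, and what remains is under 5% blasts, no Auer rods and no extramedullary disease. An early marrow in full aplasia can meet all three. The protocol uses that finding to decide on re-induction and then waits; it asks about remission later. SAP 3.2 separates the two findings only by a date, with a limited reversal. If the date does not separate them, a patient who never reaches a remission evaluation with a favourable marrow can be scored as a composite responder. That patient would then escape the EFS induction-failure rule, enter the LFS set and contribute a duration of composite CR.

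**Working it through.** **1. The plan's own figure.** SAP 2.6 gives 71.8% power for 25 per arm, 0.55 versus 0.80, Fisher's exact test at one-sided 0.15. Summing Bin(c; 25, 0.55) × Bin(e; 25, 0.80) over all tables with one-sided p ≤ 0.15 gives 71.7%, so it is reproduced. It concerns primary CR; the documents give no figure for composite CR. It confirms the test used in step 6.

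**2. Which interim marrows pass the floor.** SAP 6.1 sets Day 1 at randomization, with study day = elapsed days + 1. Table 6—1 puts randomization and first dose on Day 1. The wording of the floor can mean study Day 21, or 21 elapsed days (study Day 22).

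| Interim marrow | Study days | Passes if floor is Day 21 | Passes if floor is Day 22 |
|---|---|---|---|
| First early marrow | 14-20 | none | none |
| First early marrow | 21 | yes | no |
| 7-day repeat | 14+7=21 to 21+7=28 | all 8 days | 7 of 8 days |
| Re-induction early marrow | earliest 14+14−1=27 | all | all |

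The re-induction row assumes the earliest case: re-induction starts on the day of a Day 14 marrow, and its own early marrow is on its Day 14.

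**3. What the reversal rule catches.** It ends at Day 42, and the evaluation after re-induction is at about Day 49, so it stops 49 − 42 = 7 days too soon. Inside the window it names progression or treatment failure only. A later marrow with more than 5% but less than 20% blasts reverses a primary CR but is not marrow progression.

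**4. A worked record.** Re-induction starts on study Day 20. Its early marrow is on its Day 17, which is study Day 20+17−1=36, and shows 2% blasts with ANC 0, no Auer rods and no extramedullary disease.
- This meets Appendix A's CRi and passes the floor on either reading.
- The Day 49 evaluation shows 40% blasts. That is above 1.5 × 2% = 3% and above 20%, so it is progression, but 49 > 42 and nothing is reversed.
- Read literally, composite CR = yes. The patient enters the LFS set with a composite CR lasting 49 − 36 = 13 days, although the only remission evaluation was negative.

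**5. Size under assumptions (first induction only).** None of these inputs is in the documents: 75% leukemia-free at the early marrow; early marrow spread evenly over the 8 days; repeat probability r of 0.10 to 0.20; share q of leukemia-free patients with no later remission of 0.10 to 0.20. Excess = 0.75 × q × P(last early marrow on or after the floor).
- Floor Day 21, P = r + (1−r)/8. Low: 0.75 × 0.10 × 0.2125 = 1.6 points. High: 0.75 × 0.20 × 0.300 = 4.5 points.
- Floor Day 22, P = 7r/8. Low: 0.75 × 0.10 × 0.0875 = 0.7 points. High: 0.75 × 0.20 × 0.175 = 2.6 points.

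In 25 patients this is about 0.2 to 1.1. Leaving out re-induction makes it too low; leaving out reversals by Day 42 makes it too high. It is an illustration, not a bound.

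**6. What one patient can do.** If composite CR is tested at one-sided 15%, as SAP 8 implies, 14 versus 18 responders of 25 gives p = 0.189 and 14 versus 19 gives p = 0.116.

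**The case against.** The best defence is that the protocol keeps the two steps apart: the Days 14-21 marrow decides on re-induction, and remission is judged later. A patient who stays aplastic should have a marrow at about Day 35 or 42, and if it is clear, CRi is then properly assigned. For such patients early scoring changes only the date. This stands and limits the number affected. It does not close the gap, because SAP 3.2 states a date rule and does not refer to the remission evaluation.

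It can also be said that treatment failure in the reversal rule covers a marrow above 5% blasts. The composite bullet does not say so, and SAP 3.1 lists treatment failure and >5% blasts as separate grounds.

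Several stronger readings are tempting but not supported:
- **That a clear Day 21 marrow followed by death in aplasia on Day 33 is a composite CR.** Appendix A classes death before the end-of-Cycle-1 assessment as indeterminate, and the EFS bullet can be read as making death a treatment failure, which would reverse it. The SAP does not say which rule governs.
- **That the result depends broadly on the day of the first early marrow.** Only Day 21 matters, and not even that day if elapsed days are meant.
- **That the excess is 7.5 to 15 points.** That is 0.75 × 0.10 to 0.75 × 0.20, and needs every early marrow on Day 21, the Day 21 reading of the floor and no reversals.
- **That the open-label design biases the arms.** Nothing shows that marrow timing differs by arm. With a true rate of 0.60 in both arms (assumed) and one eighth of a 10% aplastic group counted in each, the false-positive rate is 9.6%, against 9.7% with none counted.
- **That the table shells confirm the gap.** The response list in shell 14.3.2.2.1 is too poorly legible to show what it lacks.

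**Conclusion.** The point holds in limited form. As written, SAP 3.2 can score an interim leukemia-free marrow as composite CR. The exposure lies mainly in the 7-day repeat marrow and the re-induction early marrow, and the reversal rule corrects it only in part. This is more than a missing detail: the stated floor and the Day 42 cut-off can give a wrong status when followed exactly, as the worked record shows.

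CRi, composite CR, the EFS induction-failure rule, the LFS set and duration of composite CR are affected. Primary morphologic CR is not, because it requires ANC above 1000/µL and platelets above 100,000/µL. The size cannot be known from the documents, and the range in step 5 rests wholly on assumed inputs. A difference between arms is possible in principle but not shown. The plan should be changed, but the point does not threaten the primary analysis.

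**What to change.** In SAP 3.2:
- Assign CRi and CRp only at the protocol's remission evaluation: at count recovery, or at the scheduled no-recovery evaluation after induction or re-induction. Protocol 6.4.1 puts the latter at about Day 35 or 49, while Table 6—1 has a Day 42 marrow; these must be reconciled so that the SAP can name the qualifying marrow.
- Classify a marrow under 5% blasts from the Days 14-21 assessment or its 7-day repeat, in either cycle, as leukemia-free state and never by itself as composite CR.
- Use the primary endpoint's >5% blast reversal wording, and run the window through the evaluation after re-induction.
- State that death before the remission evaluation is not a composite CR.
- Carry the same rule into EFS and LFS.

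The cost is SAP wording and one derivation flag from the visit label and marrow date already collected; no patient's treatment changes. Composite CR may fall slightly in all arms. The fix does not add a count minimum to CRi at the remission evaluation. Appendix A allows CRi without one, and the repair concerns only which marrow may carry the label.

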3.3 Safety Endpoints

Key safety endpoints will be assessed by review of summaries of AEs which will include only treatment-emergent AEs (TEAEs), unless otherwise stated. Adverse events will be categorized by System Organ Class (SOC) and preferred term using the Medical Dictionary for Regulatory Activities (MedDRA) dictionary (version 14.1), and will be graded according to NCI-CTCAE version 4.03.

4 PHARMACOKINETIC/PHARMACODYNAMIC VARIABLES

Details to be provided by Biocascade in a separate PK SAP.

5 ANALYSIS POPULATIONS

The analysis sets that will be used for statistical analyses are as follows:

Intent-To-Treat (ITT): This includes all randomized patients. Patients will be analyzed according to the treatment to which they are randomized. The ITT Population will be the primary analysis set for the efficacy variables.

modified-Intent-To-Treat (mITT): This includes all randomized patients who received at least one dosage of study drug. Patients will be analyzed according to the treatment to which they are randomized.

Per Protocol (PP): Supporting analyses will be conducted on the PP Population, comprising all patients randomized and treated without major protocol deviations during the trial. This population will be documented before final database lock. PP Population will be analyzed according to the treatment to which they received.

The following are considered protocol deviations for the purpose of identifying the per protocol set:

1. Patients who were subsequently found to be not complying with the inclusion and exclusion criteria
2. Patients who are not compliant with study restrictions (eg. use of prohibited medication (generic drug name) or prohibited treatment therapy)
3. Patients who continued in study but should have been withdrawn according to withdrawal criteria
4. Patients who are not compliant with study drug treatment dose modification or stoppage rules (either temporary or permanent).
5. Patients who took incorrect study drug (CX-01 or other) dose, frequency, timing or method of drug delivery (e.g. subject overdosed with study drug, incomplete study drug administered).

6. Patients who took different study drug than the study drug to which they were randomized.
7. Patients who do not have post baseline data anywhere in the system.

Items 1 to 5 are routinely monitored in the study as part of the study monitoring plan.

Safety: All patients who received at least one dose of study treatment. Patients will be included in the analyses according to the treatment they received. The Safety Population will be used in the analyses of all safety endpoints.

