- Idarubicin 12 mg/m²/day by slow (10 to 30 minutes) IV injection/infusion daily on Days 1 and 2
- Cytarabine 100 mg/m²/day by continuous 24-hour IV infusion on Days 1-5.

Group 2: Idarubicin + Cytarabine + plus lower dose CX-01

- CX-01 given as a 4 mg/kg initial bolus on Day 1, 30 minutes after completion of administration of the first dose of idarubicin followed by CX-01 0.125 mg/kg/hour as a continuous 24-hour IV infusion on Days 1-5
- Idarubicin 12 mg/m²/day by slow (10 to 30 minutes) IV injection/infusion daily on Days 1 and 2
- Cytarabine 100 mg/m²/day by continuous 24-hour IV infusion on Days 1-5.

Group 3: Idarubicin + Cytarabine + plus higher dose CX-01

- CX-01 given as a 4 mg/kg initial bolus on Day 1, 30 minutes after completion of administration of the first dose of idarubicin followed by CX-01 0.25 mg/kg/hour as a continuous 24-hour IV infusion on Days 1-5
- Idarubicin 12 mg/m²/day by slow (10 to 30 minutes) IV injection/infusion daily on Days 1 and 2
- Cytarabine 100 mg/m²/day by continuous 24-hour IV infusion on Days 1-5.

Consolidation Therapy

Evaluation for remission will take place at the time of count recovery, or, if no count recovery is achieved, at approximately Day 35 if the patient received one induction course or approximately Day 49 if the patient received re-induction course. Count recovery is defined as ANC >1,000/μL and platelet count of >100,000/μL. Remission will be defined according to IWG criteria (Appendix A). For patients with documented CR, confirmatory bone marrow aspirate slides will be submitted to the Sponsor or designee.

Patients in remission at the end of induction may proceed to consolidation therapy on study, depending upon factors including, but not limited to, European Leukemia Net (ELN) (70) genetic risk and co-existing conditions.

Patients who are not in CR at the end of re-induction will be taken off study and will complete Early Termination Visit as per Table 6—1.

Patients who could benefit from and are eligible to undergo stem cell transplantation will go off the study at any time when transplant is feasible.

Patients will receive up to two cycles of consolidation therapy on study, per NCCN guidelines, depending upon factors including, but not limited to, ELN genetic risk and co-existing conditions. A cycle of consolidation therapy is defined as the time from initiation of chemotherapy on Day 1 until count recovery.

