6.8.2 Patient Populations Analyzed

The analysis sets that will be used for statistical analyses are as follows:

Intent-To-Treat (ITT): All randomized patients. Patients will be analyzed according to the treatment to which they are randomized. The ITT Population will be the primary analysis set for the efficacy variables.

Per Protocol (PP): Supporting analyses will be conducted on the PP Population, comprising all patients randomized and treated without major protocol violations during the trial. This population will be documented before final database lock.

Safety: All patients who received at least one dose of study treatment. Patients will be included in the analyses according to the treatment they received. The Safety Population will be used in the analyses of all safety endpoints.

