7.6.2 Secondary Efficacy Analysis

The primary efficacy analysis will be repeated using the PP Population as a supportive analysis along with CRi and composite CR for ITT and PP. Complete response rates and composite complete response rates and confidence intervals will also be reported for key subgroups (De-novo vs secondary AML at diagnosis, Age < 70 vs Age ≥ 70, ECOG performance status = 1 vs ECOG performance status = 2). The following secondary analyses will be performed on the ITT population. Analyses of EFS, LFS, time to neutrophil and platelet recovery, and OS will be descriptive. Kaplan-Meier (KM) estimates will be used to estimate the survival distribution for each arm and KM plots will be produced to accompany these analyses. 95% Confidence Intervals will be reported for medians and KM estimates. Duration of response will be analyzed using a similar approach; the survival distributions will be estimated as cumulative incidence functions.

Statistical Analysis Plan

Version: Final

Date of Issue: 20 March 2018

Cantcx Pharmaceuticals, Inc. Protocol No. CNTX-CX-01 2015 AML I Covance Study ID: 0000014620 I

Mortality rate at Day 30, Day 60, and Day 90 will be reported using descriptive statistics in a manner similar to the reporting of the morphologic CR rate. The time to neutrophil and platelet recoveries will be reported using the following descriptive statistics: N, mean, SD, median, minimum, maximum, and the 1st and 3rd quartiles.

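### The per-protocol set counts major deviations over the whole trial, so deviations in consolidation can remove patients whose remission is already scored and bias the supportive CR, CRi and composite CR tests

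*SAP*

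**What the plan says.** - **PP set.** SAP 5 describes it as "comprising all patients randomized and treated without major protocol deviations during the trial". Protocol 6.8.2 uses the same open span: "comprising all patients randomized and treated without major protocol violations during the trial". Neither gives a cut-off date or cycle.
- **What counts as a deviation.** The SAP 5 list includes "Patients who took incorrect study drug (CX-01 or other) dose, frequency, timing or method of drug delivery" and "Patients who are not compliant with study drug treatment dose modification or stoppage rules (either temporary or permanent". Neither item is limited to induction.
- **Use of the set.** SAP 7.6.2: "The primary efficacy analysis will be repeated using the PP Population as a supportive analysis along with CRi and composite CR".
- **When the outcome is scored.** SAP 3.1 counts patients "achieving morphological CR based on IWG criteria during the induction and re-induction phases of the treatment".
- **Who reaches consolidation.** Protocol 6.4.1: "Patients in remission at the end of induction may proceed to consolidation therapy on study". On the others it says: "Patients who are not in CR at the end of re-induction will be taken off study".
- **What consolidation involves.** Under Protocol 6.4.1, control patients receive cytarabine alone. Groups 2 and 3 add a timed CX-01 bolus and a 120-hour infusion. Protocol 6.4.4.2 permits cytarabine reduction in consolidation and sets hold, reduction and stopping rules for CX-01.

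**The concern.** A per-protocol analysis of a response endpoint should depend on adherence up to the time the response is determined. Here, membership also depends on events that come later and that are open almost only to responders. A patient can reach CR, go on to consolidation, have a major dosing deviation there, and drop out of both numerator and denominator of the PP response rate. A patient taken off study for lack of remission has no such exposure.

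The effect within an arm has a known direction: the PP response rate falls. The effect on the comparison depends on whether the arms differ in major consolidation deviations. The CX-01 arms have an additional drug and additional rules to follow, so a difference is plausible. If it occurred, a benefit seen in the ITT analysis could look less well supported in PP for a reason unrelated to induction treatment.

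**Working it through.** **Inputs from the plan** (Protocol 6.8.1, SAP 2.6): 25 evaluable patients per arm, CR 0.55 on control and 0.80 on CX-01, one-sided Fisher exact test at 0.15, stated power 71.8%.

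**Reproducing the plan's figure.** Enumerating all pairs of counts from two independent Binomial(25) arms gives 71.7%, in agreement with the stated value. With 0.55 in both arms the rejection probability is 10.0%.

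**Assumed inputs** (the documents give none):
- c = 0.70, the share of remitters consolidated on study
- d, the share of those with a major deviation in consolidation, varied by arm
- no exclusions for induction-phase deviations
- every deleted patient counts as a CR

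**Formulas.** With q = c × d and true CR rate p:
- PP CR rate = p(1 − q) / (1 − pq)
- PP odds ratio = true odds ratio × (1 − q for CX-01) / (1 − q for control)
- True odds ratio = (0.80/0.20) / (0.55/0.45) = 3.27

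**Worked case, d = 30% (CX-01) versus 10% (control).** q = 0.21 and 0.07.
- Expected deletions: 25 × 0.80 × 0.21 = 4.2 on CX-01; 25 × 0.55 × 0.07 = 0.96 on control
- CX-01 PP rate: 0.80 × 0.79 / (1 − 0.168) = 0.632/0.832 = 0.760
- Control PP rate: 0.55 × 0.93 / (1 − 0.0385) = 0.5115/0.9615 = 0.532
- PP odds ratio: 3.27 × 0.79/0.93 = 2.78

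**Range** (exact enumeration of the Fisher test after deletion):

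| d, CX-01 / control | PP CR, CX-01 / control | Difference | Odds ratio | Chance PP meets 15% |
|---|---|---|---|---|
| none | 0.800 / 0.550 | 0.250 | 3.27 | 71.7% |
| 20% / 20% | 0.775 / 0.512 | 0.262 | 3.27 | 70% |
| 15% / 10% | 0.782 / 0.532 | 0.250 | 3.15 | 69% |
| 20% / 10% | 0.775 / 0.532 | 0.243 | 3.03 | 66% |
| 30% / 10% | 0.760 / 0.532 | 0.228 | 2.78 | 60% |
| 40% / 10% | 0.742 / 0.532 | 0.210 | 2.53 | 54% |

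**Selection versus smaller numbers.** At 30% versus 10% the chance is 60.3%. Removing the same expected numbers at random gives 67.6%. Of the 11.4 points lost, 71.7 − 67.6 = 4.1 come from fewer patients and 67.6 − 60.3 = 7.3 from selection.

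**No true effect** (0.55 in both arms, 30% versus 10%): the CX-01 PP rate is 0.55 × 0.79 / (1 − 0.1155) = 0.491 against 0.532, a spurious difference of about −4 points.

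**One data set.** 20/25 versus 14/25 gives one-sided p = 0.064. Deleting four CX-01 remitters gives 16/21 versus 14/25, p = 0.131, still under 0.15. Deleting six gives 14/19 versus 14/25, p = 0.187, which fails.

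**Offset.** Let s be the share of non-remitters excluded for induction deviations. Then the PP rate = p(1 − q) / [p(1 − q) + (1 − p)(1 − s)], with q kept at 0.21 and 0.07.
- s = 21% / 7%: the rates return to 0.800 and 0.550.
- s = 30% / 10%: CX-01 = 0.632 / (0.632 + 0.20 × 0.70) = 0.819; control = 0.5115 / (0.5115 + 0.45 × 0.90) = 0.558. The difference is 0.261, now above the true 0.25.

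**With a cut-off at the response assessment**, q = 0 in both arms. The chance returns to 71.7%, before any induction-phase exclusions.

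**The case against.** A reader might infer that the rule necessarily tilts PP against CX-01. The documents do not support that. They give no deviation rates. Exclusion requires a deviation judged major, which SAP 5 does not define beyond its list. Much CX-01 interruption is foreseen: Protocol 6.4.1.5 provides for interrupted infusions and Protocol 6.4.4.2 prescribes holds and reductions, so following those rules is not non-compliance. At equal rates the odds ratio does not move and the difference widens slightly. The net direction is also open, because induction is more complex on CX-01 too, and excluding non-remitters for induction deviations pushes the other way.

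A reader might also infer that a non-CR patient can never be removed through consolidation. That is too absolute. SAP 3.1 lets a CR be superseded up to day 42 from randomization, while Protocol 6.4.1 lets consolidation start from day 28 of induction. The remission wording there could also admit some CRi patients.

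Finally, the impact is limited. ITT carries the primary fixed-sequence test and PP gates nothing. An mITT table of CR is planned (Table 14.2.2), which this rule cannot affect. SAP 7.3 lists and summarizes by arm the deviations that lead to PP exclusion, so deletions would be visible.

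All of this stands as a limit on direction and size. It does not remove the defect: no section restricts PP deviations to those before the response assessment. A possible offset of unknown size does not make the supportive analysis sound.

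**Conclusion.** The concern holds in conditional form. As written, PP membership for the CR, CRi and composite CR analyses can depend on events after the outcome is determined, and those events fall almost only on remitters. This lowers the PP response rate in any arm where it happens.

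Bias in the comparison needs unequal major-deviation rates in consolidation. Under the assumptions above, the loss in the chance of meeting the 15% criterion runs from under 2 points at equal 20% rates, through about 5 points at 20% versus 10%, to about 11 points at 30% versus 10%, part of which reflects smaller numbers only. None of these rates comes from the documents, and induction-phase exclusions could cancel or reverse the effect. Only the supportive PP tests are touched; the ITT primary test is not.

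**What to change.** In SAP 5, state that for the PP analyses of CR, CRi and composite CR only major deviations dated on or before the response assessment that determines the patient's induction or re-induction outcome lead to exclusion. Tying the cut-off to that assessment also handles a CR that is superseded by day 42. Summarize later deviations separately by arm.

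Keep the whole-trial PP set, as a second defined set, for OS, EFS, LFS and remission duration, for which PP tables are listed in the shells.

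The cost is one or two sentences in SAP 5, a date filter, and two PP sets to label and document before database lock. It also requires that deviation dates be available. The readable text does not show whether they are recorded, so this should be confirmed. The primary analysis does not change.
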